1.5 Sample Size Justification

Primary outcome:

Rate of decline in viral load. We expect a gradual decay in viral loads (depending on when in the infection's natural history participants are enrolled. Participants will be detected as being SARS-CoV-2-positive by our screen at varying points in the infection (some early, some late). Based on the 4 manuscripts with measurements, including Hung et al ³¹ and Gautret et al ¹⁹, we can calculate an expected decline rate. One outcome would be a greater than expected fall in viral load in the active arms vs the SoC arm (e.g., 0.3 log₁₀ /day greater decline =0.9 log₁₀ in 3 days).

We will compare rate of decline in viral load Arm 1 (NTZ, RBV + HCQ) to Arm 2 (placebo) with the aim of determining if the combination of NTZ, RBV + HCQ is superior to placebo. We plan to enroll 35 participants in each arm of the trial for a total of 70. We assume data are collected at baseline and 3, 6 and 10 days after enrollment.

Power calculations were obtained from simulated data, where:

- Baseline log10 VL was generated from uniform (3,9) distribution (i.e., at baseline, people were equally likely to have log10 VL anywhere from 3 to 9. This is consistent with Hung et al ³¹
- For the control group, average change per day was set to either -0.3 or -0.4. In Hung et al ³¹ it appears to be about -0.37.
- For the treatment group, the average decline per day was greater (steeper) than the control group by either 0.2 or 0.3. In Hung et al ³¹the difference in slopes appears to be about 0.2
- Within person SD was set to either 0.5 or 1.
- SD of the slope between individuals was set to 0.2. In Hung et al ³¹ the within-group IQR of log10 VL was relatively small, so we do not expect a large amount of variation in slopes between participants.

Power was calculated using the following steps: (1) generate 1000 data sets in each scenario; (2) fit random slope and intercept models to the simulated data; (3) record the proportion of times that the test of the interaction between treatment and slope was rejected.

		treatment effect		
Slope SoC group	SD	-0.2	-0.3	
-0.3	0.5	94	99	
-0.4	0.5	94	99	
-0.3	1	87	99	
-0.4	1	84	99	

Results: Power (%) based on a sample size of 30 per group

In all of these scenarios we would have >80% power to detect a difference in the slope between groups.

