6.0 Data Management Plan

6.1 Data Analysis

We will follow intention-to-treat principles and analyze the groups as randomized. A summary table of baseline variables will be created with means and standard deviations for continuous variables or percentages for categorical variables, all stratified by treatment group.

Primary outcome. We will have repeated measures of log10 VL for each participant. These measurements will occur on day 0 (baseline) and at about days 3, 6 and 10. We will fit a linear mixed effects model, where log10 VL is the outcome, indicators for treatment group (SoC reference), time, and treatment by time interactions are the predictors. The model will include a random slope and intercept, to account for within participant correlation. The robust sandwich variance will be used to estimate standard errors. Because we are estimating within participant changes over time from randomization, we can estimate a treatment effect at any particular day. Our primary hypotheses involve the change over time, which we will assess with the treatment by time interaction terms. If participants drop out from the study

before the day 10 visit, we will use all of their preceding data. Linear mixed effects models rely on the assumption that missing data are missing at random.

Secondary outcomes. For binary outcomes, such as progression to having symptoms, intubation, death, hospitalization, and admission to intensive care unit, we will fit logistic regression models. The covariates will include the treatment group indicators. We will report odds ratios and 95% confidence intervals. For change variables, such as change in viral shedding or change in Q-T interval, we will fit linear mixed effects models (similar to primary outcome).

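### Section 6.1 names the robust sandwich for the primary test without a small-sample correction or reference distribution; at 35 per arm a nominal 5% test could run at about 5.3% to 5.8%.

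*Combined protocol and SAP*

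**What the plan says.** Section 6.1 (Data Analysis, primary outcome) fits a linear mixed model to log10 viral load at days 0, 3, 6 and 10. On the covariance it says "The model will include a random slope and intercept, to account for within participant correlation", and on the standard errors "The robust sandwich variance will be used to estimate standard errors". The test is on the interaction: "Our primary hypotheses involve the change over time, which we will assess with the treatment by time interaction terms".

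The section does not say which form of the sandwich is meant, whether the statistic is referred to a normal or a t distribution, or what alpha applies to the primary test. Change variables among the secondary outcomes, including Q-T change, are to be analysed with similar mixed models.

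Section 1.5 (Sample Size Justification) gives the size: "We plan to enroll 35 participants in each arm of the trial for a total of 70". Its power table carries the label "Power (%) based on a sample size of 30 per group". The simulation behind it is described as "fit random slope and intercept models to the simulated data", with no mention of how standard errors were obtained.

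**The concern.** The sandwich estimates the variance of the treatment effect from between-participant residuals. In its ordinary form it is biased downward when there are few independent units, because the fitted means absorb some of the residual variation. Here there are 70 units, 35 per arm. A normal critical value adds a second, separate shortfall, because it ignores the uncertainty in the estimated variance. Both push the same way, towards intervals that are too narrow and a test that rejects too often.

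At stake are the calibration of the single primary p-value and its interval, and of the secondary mixed models that follow the same approach. Because the text leaves the correction and reference open, the p-value also depends on a software default or on a choice made after the data are in.

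**Working it through.** **Inputs.** From section 1.5: 35 per arm (30 in the power table); visits at days 0, 3, 6 and 10; within-person SD 0.5 or 1; between-person slope SD 0.2; slope difference 0.2 or 0.3 log10 per day. Assumed, because the documents do not say: two-sided 5%, time entered linearly, complete data.

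**Reduction to a two-sample problem.** With complete data at common times, the interaction estimate is the difference between arms in mean per-person least-squares slope. The mean visit day is 4.75, so Sxx = 4.75² + 1.75² + 1.25² + 5.25² = 54.75. The SD of a per-person slope is sqrt(0.2² + SD²/54.75):
- SD 0.5: 0.211
- SD 1: 0.241

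**The plan's own figures first.** The documents state no type I error, so the power table is the only figure to reproduce. With a t test on 58 df at 30 per group:

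| Effect | SD | Recomputed power | Stated |
|---|---|---|---|
| 0.2 | 0.5 | 95.0% | 94, 94 |
| 0.2 | 1 | 88.4% | 87, 84 |
| 0.3 | 0.5 | 100.0% | 99, 99 |
| 0.3 | 1 | 99.7% | 99, 99 |

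Seven of the eight cells agree within 2 points. The 84 cell is 4.4 points below the recomputed value. The statement that power exceeds 80% throughout is reproduced.

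**Type I error at 35 per arm.** The ordinary sandwich divides each arm's sum of squares by n instead of n − 1, so its variance is (n − 1)/n = 34/35 of the unbiased one. The standard error is therefore multiplied by sqrt(34/35) = 0.9856. Under normality the statistic with the unbiased variance is t on 68 df, so the true size is P(|t68| > c × 0.9856), where c is the critical value used: 1.960 (normal) or 1.9955 (t68).

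| Variance | Reference | Effective cut-off | Type I error |
|---|---|---|---|
| Ordinary sandwich | normal | 1.932 | 5.76% |
| Ordinary sandwich | t68 | 1.967 | 5.33% |
| Sandwich × 70/69 | normal | 1.946 | 5.58% |
| Sandwich × 70/69 | t68 | 1.981 | 5.16% |
| Unbiased | normal | 1.960 | 5.41% |
| CR2 (unbiased here) | t68 | 1.995 | 5.00% |

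A simulation of 100,000 trials also gave 5.76% for the first row.

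**Where the excess comes from.** With the normal reference the excess is 5.76 − 5.00 = 0.76 points. The normal reference alone accounts for 5.41 − 5.00 = 0.41, and the sandwich bias adds 5.76 − 5.41 = 0.35. In a two-sided test this is 0.76/2 = 0.38 points in each tail.

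**Intervals.** Coverage is 100 − 5.76 = 94.2% (normal) or 100 − 5.33 = 94.7% (t). Relative to a correct interval, the width is 1.960 × 0.9856/1.9955 = 0.968, or 3.2% too narrow, with the normal reference. It is 0.9856, or 1.4% too narrow, with t.

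**Sensitivity.** An assumed 15% dropout moved the simulated size by only 0.1 to 0.2 points (8,000 trials, Monte Carlo SE about 0.26 points). Linear time matters more: if time were entered as visit indicators and the three interaction terms tested jointly, an uncorrected chi-square Wald test would run at about 7.1%.

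**The case against.** The strongest reply is that the plan never says the sandwich is uncorrected or the reference normal. It is silent, and a small-sample version with a t reference fits its sentence. That stands: 5.8% is the top of a range from 5.0% to 5.8%, not what the plan is shown to do. But every combination in the table short of CR2 with t exceeds 5%, so the silence is worth closing.

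It can also be said that a sandwich is a sensible choice, since it protects against a misspecified covariance, a real possibility for viral loads with a limit of quantification. That stands too, and the remedy should keep that protection.

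A reader might infer more than the documents support:
- **That the error favours treatment.** The excess is symmetric under a two-sided test, so a false finding of harm is as likely as one of benefit.
- **That it damages a symptom-stratum analysis.** Randomization is stratified by symptoms, but section 6.1 plans no mixed model within strata.
- **That the powered test differs from the stated one.** Section 1.5 does not mention standard errors. Silence there does not show a different method.
- **That a Kenward-Roger analysis would do equally well.** It is model-based and gives up the robustness the sponsor chose.

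**Conclusion.** The point holds as a small calibration gap. With the ordinary sandwich at 35 per arm, the primary test would run at about 5.3% (t reference) to 5.8% (normal reference). This rests on a two-sided 5% level, linear time, complete data and normal errors. Sandwich bias accounts for less than half of the upper figure's excess. At under one percentage point it does not threaten the primary conclusion, but it sits on the only primary test and is easily removed.

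**What to change.** Replace the standard-error sentence in section 6.1 with: *Standard errors will use the bias-reduced (CR2) sandwich estimator clustered on participant, with Satterthwaite degrees of freedom and a t reference distribution; this applies to the primary and secondary mixed models.* The same passage should state alpha and sidedness for the primary test and confirm that time is linear, since the figures above assume both.

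With complete, balanced, normal data this gives exactly 5.0%; with dropout it is approximate. The cost is one sentence and a standard software option. At 35 per arm, SD 1 and effect 0.2, nominal power falls from 93.6% (ordinary sandwich, normal reference) to 92.7%, about 0.9 points. Intervals become 1/0.9856 = 1.015 to 1/0.968 = 1.033 times as wide, so about 1% to 3% wider. Power stays well above 80%.

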1.3 Research Design and Methods

We will conduct a randomized clinical trial enrolling eligible participants who are determined to be SARS-CoV-2-positive (e.g., via Rutgers Corona Cohort [RCC] study, hospital or other screening programs) who volunteer for the study. Specifically, we will enroll 70 participants whose test has been performed within the past 7 days who are either asymptomatic or mildly symptomatic at baseline. Mild COVID-19 symptoms include new cough, sore throat, fever, myalgias, new vomiting or diarrheaor change in smell or taste. Illness requiring hospitalization, or those who present with hypoxia (PO2<92%) or shortness of breath at time of enrollment will be classified as significantly symptomatic and excluded from study participation. People who are allergic or intolerant to NTZ, RBV or HCQ will be excluded. We will randomly allocate participants stratified by presence of mild symptoms to 1) NTZ, RBV and HCQ or 2) placebo. Treatment with the investigational agents or placebo will continue for 5 days. Viral load will be assessed at baseline (day 0) as well as at days 3, 6, and 10 to monitor response to antiviral treatment. Immune status will be determined by antibody testing of blood collected at baseline and day 28.

Prior to initiating enrollment, we will prepare two randomization tables for treatment assignment using permuted blocks of six which will be provided to the research pharmacist. One table will be used for participants without symptoms and the other will be used for those with mild symptoms. The pharmacist will prepare kits containing the 5-day supply of study medications (investigational drugs/placebo) which will be sequentially numbered in accordance with the randomization tables. The contents of each kit (investigation drugs/placebo) will be indistinguishable. Study staff will establish symptom status at the baseline visit, and per pharmacy order, provide the participant the next numbered medication kit in the participant's stratum (no symptoms/mild symptoms). The study investigators, staff interacting with the participants are all masked to treatment assignment

A. Research Procedures

- 1. Study Procedures:
 - Day 0/1 Screening/Baseline Visit (in person)
 - Pre-screen via online screening form to confirm eligibility
 - Obtain informed consent for trial enrollment
 - Medical history
 - Medication history
 - Document symptoms (if any)

- o Take temperature, PO2, Pulse
- Q-T interval assessment

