 Adverse Events Based on Signs and Symptoms When collecting AEs, the recording of diagnoses is preferred (when possible) to recording a list of signs and symptoms. However, if a diagnosis is known and there are other signs or symptoms that are not generally part of the diagnosis, the diagnosis and each sign or symptom will be recorded separately.

D. Data Points

Case Report Forms

Completion of the electronic case report forms (eCRFs) will be done in accordance with the instructions outlined in the study specific data capture plan. All eCRFs are considered the primary

data collection document for the study and are stored in REDCap in a confidential format. Only key personnel who are delegated in the delegation of authority log are permitted to make entries, changes, or corrections in the eCRF. All users will complete user training, as required or appropriate per regulations. An audit trail will be maintained automatically by the electronic CRF management system.

Data Points to be collected:

- Baseline medical history
- Treatment compliance
- Daily temperatures
- Symptoms of disease
- Adverse events
- Concomitant medications
- Any standard of care treatments or procedures to manage COVID-19
- Viral load from saliva specimen
- Viral load from mid-turbinate self-nasal swab
- SARS-CoV-2 infections confirmed or suspected in household members

Data Submission Timeline and Forms

Completion of eCRFs will occur within 72 hours of study time point unless otherwise indicated. Baseline (pre-study) eCRFs (e.g., enrollment, medical history, concomitant medications, etc.) will be completed no later than 24 hours after the start of treatment.

E. Study Duration

Study participants will be treated for five (5) days and will then remain on follow-up for up to 28 days after entry into the study. The estimated time to complete the entire study including data analysis is 3-6 months

F. Endpoints

Primary endpoint:

1. Rate of decline in viral load over the 10 days after randomization

Secondary:

- 1. Proportion of participants with virus below LLOQ at day 10
- 2. Proportion of participants asymptomatic at day 10.
- For those who were asymptomatic at baseline: Progression to symptoms--presence or absence of key symptoms: fever ≥ 100.4^o F (38 ^o C); sore throat, cough, shortness of breath, myalgias, vomiting or diarrhea, or change in smell or taste

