- 4. Proportion of participants with progression of severity of COVID-19 symptoms (hospitalization and length of stay; admission to intensive care unit and number of days in unit; Intubation; Death (any cause))
- 5. Comparison of severity of disease in participants who develop symptoms of COVID-19 at all timepoints
- 6. Assessment of medication toxicity as measured by standard metrics
- 7. Q-T interval from baseline of > 60msec or QT > 500 msec)
- 8. Number of participants with undetectable viral load and absence of symptoms
- 9. Rate of decline in viral load at study days 3 and 6
- 10. New, self-reported COVID infection in household members

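### Ordinary logistic regression is planned for death, intubation and ICU admission with 35 per arm and no sparse-event method, so an arm with no events would leave no finite odds ratio; for hospitalization this depends on the event rate.

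*Combined protocol and SAP*

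**What the plan says.** Section 6.1 (Data Analysis, secondary outcomes) lists the binary outcomes one by one. For progression to symptoms and for "intubation, death, hospitalization, and admission to intensive care unit, we will fit logistic regression models". On model terms it says: "The covariates will include the treatment group indicators"; no other term is named. On reporting it says: "We will report odds ratios and 95% confidence intervals".

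Section 1.5 sets the size: "We plan to enroll 35 participants in each arm of the trial for a total of 70". Section 1.3 enrolls people "who are either asymptomatic or mildly symptomatic at baseline". It also states: "Illness requiring hospitalization, or those who present with hypoxia (PO2<92%) or shortness of breath at time of enrollment will be classified as significantly symptomatic", and such people are excluded. Participants are treated for five days and "will then remain on follow-up for up to 28 days after entry into the study".

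Section 1.3 F (Endpoints) words secondary endpoint 4 differently from 6.1. It is a proportion of participants whose illness progresses in severity, followed in brackets by "hospitalization and length of stay; admission to intensive care unit and number of days in unit; Intubation; Death (any cause".

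The documents give no expected rate for any of these outcomes. They specify no exact test, penalized fit, risk difference or descriptive fallback for sparse data.

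**The concern.** The entry criteria remove the participants most likely to deteriorate, follow-up is short and each arm is small. Death, intubation and ICU admission may therefore produce no events in one arm, or in either.

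If one arm is empty, the maximum-likelihood odds ratio is zero or infinite, and the Wald interval reflects only where the software stopped iterating. If both arms are empty, the odds ratio is undefined. The planned report would then contain either nothing or a spurious number, and the replacement method would be chosen after the data had been seen. These outcomes are components of secondary objective 4, the trial's measure of clinical progression.

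**Working it through.** The documents state no rate, power or precision for the binary clinical outcomes. The only power calculation (section 1.5) concerns the viral-load slope, so there is no figure of the plan's own to reproduce here.

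**Inputs.** n = 35 per arm (section 1.5). Logistic regression on treatment, with an odds ratio and 95% CI (section 6.1). Per-arm risk p is not given, so a range is assumed.

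**Formulas.** The chance of no events in one arm is q = (1 − p)^35. With equal risks, the chance that at least one arm is empty is 1 − (1 − q)², and the chance that both are empty is q².

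Example at p = 1%: q = 0.99^35 = 0.703; 1 − 0.297² = 0.912; 0.703² = 0.495.

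| Assumed risk, both arms | At least one arm empty | Both arms empty |
|---|---|---|
| 0.5% | 97% | 70% |
| 1% | 91% | 49% |
| 2% | 74% | 24% |
| 3% | 57% | 12% |
| 5% | 30% | 3% |
| 10% | 5% | 0.1% |

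(Last cell: 0.9^35 = 0.025, and 0.025² = 0.0006.)

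**Crossover.** Setting 1 − (1 − q)² = 0.5 gives q = 0.293, so p = 1 − 0.293^(1/35), about 3.4%. An empty arm is more likely than not only below that risk.

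**If treatment halves the risk.** The chance is 1 − (1 − q₁)(1 − q₂):
- 2% vs 1%: 85%
- 5% vs 2.5%: 51%
- 10% vs 5%: 19%

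**What the planned fit returns.** Take 2/35 on placebo and 0/35 on active treatment. One standard maximum-likelihood routine does not converge (log odds ratio about −29, standard error about 1.3 million). Another stops at −20.8 with standard error 13,432. The same data give two different meaningless answers.

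**What other methods return.**
- 2/35 vs 0/35: the exact conditional odds ratio is 0, with 95% CI 0 to 5.30. Fisher's exact p = 2 × (35 × 34)/(70 × 69) = 0.49. The Firth estimate, which in a two-by-two table equals adding 0.5 to each cell, is (0.5/35.5)/(2.5/33.5) = 0.19, with 95% CI 0.009 to 4.08.
- 1/35 vs 0/35: the exact interval is 0 to 39. The Firth estimate is 0.32 (0.013 to 8.23).
- 0/35 vs 0/35: there is no maximum-likelihood or exact conditional odds ratio. Counts still inform: the exact two-sided 95% upper limit for 0/35 is 1 − 0.025^(1/35), about 10%.

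**The case against.** **The event rates are assumed.** This is true, and it limits the point most for hospitalization. A reader might infer that all four outcomes are likely to fail. The documents do not support that: they give no hospitalization rate, and at 5% or 10% per arm an empty arm is the less likely result. For death, intubation and ICU admission the case needs only risks of about 2% or less, which is a modest assumption in this population.

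**Section 6.1 names neither maximum likelihood nor Wald intervals.** Exact and Firth-penalized fits are also logistic regression, and both give an interval when one arm is empty. A reader might therefore go too far in concluding that the promised estimate cannot exist under any reading of the plan. What stands is that ordinary maximum likelihood is the usual meaning of the wording, and that no alternative is named.

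**Endpoint 4 may already be a composite.** Section 1.3 F can be read as one proportion of participants who progress. Its frequency would then be at least that of hospitalization, where the problem is weakest. Objective 4 also covers hospital and ICU days, which are not logistic outcomes. It would therefore be wrong to infer that objective 4 as a whole would yield nothing usable. However, 6.1 lists the components separately, so the two sections need to be reconciled.

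**The consequences are small.** These are secondary outcomes with no power claim, an analyst would notice standard errors of that size, and no method extracts much from 2 events against 0. All of this is fair. It bears on severity and does not supply the missing method.

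**Conclusion.** The concern holds for death, intubation and ICU admission. Followed on its usual reading, the plan has a 74% to 97% chance of meeting an empty arm for each such outcome whose risk lies between 2% and 0.5% per arm, and it would then yield no finite odds ratio or usable Wald interval. For hospitalization it is conditional: more likely than not below about 3.4% per arm, about 30% at 5% and about 5% at 10%. These figures assume 35 analyzed per arm and equal risks; a treatment benefit that lowers the risk in the active arm raises them.

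The point does not extend to progression to symptoms, which may be common, or to the primary slope analysis. It is worth correcting before analysis, but it does not threaten the trial's main conclusion.

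**What to change.** In section 6.1, separate rare from common binary outcomes.

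- For death, intubation and ICU admission, and for hospitalization if events are few, report counts per arm and the risk difference with an exact or score 95% CI, with Fisher's exact test. If an odds ratio is wanted, name Firth-penalized or exact logistic regression. Define in advance what counts as few, and say that only counts with exact intervals for the proportions will be given when both arms have none.
- Keep ordinary logistic regression for the common binary outcomes.
- Reconcile 6.1 with secondary endpoint 4 in 1.3 F by stating whether the compared measure is the composite of hospitalization, ICU admission, intubation or death, or each component. A composite is at least as frequent as hospitalization, but it does not by itself remove the need for a sparse-event method.

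**Cost.** The change of estimator is analysis wording only; enrollment, visits and data collection stay as they are. Settling the composite also fixes an endpoint definition, so 1.3 F must be amended with 6.1. Exact methods are slightly conservative, and intervals will be wide whichever method is chosen.

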QT interval will be measured on an ongoing basis through day 10 via the Zio AT mobile cardiac telemetry device describe in section 4.7 E. If the corrected QT - QTc interval increases from baseline of > 60msec or QT > 500 msec, the medications, if still being taken, will discontinued at that time. Participant QTc intervals will be monitored every 6 hours until the interval returns to baseline. If a serous arrhythmia is detected during the continuous monitoring, the study cardiologist and participant will be promptly contacted, and the participant will be directed to seek medical treatment as appropriate.

C. Study Safety Assessments

The Principal Investigator is responsible for ensuring that all staff involved in the study are familiar with the content of this section.

- 1. Definitions:
 - Adverse Events:

An adverse event is the development of an undesirable medical condition or the deterioration of a pre-existing medical condition following or during exposure to a pharmaceutical product, whether considered causally related to the product. An undesirable medical condition can be symptoms (e.g., nausea, chest pain), signs (e.g., tachycardia, enlarged liver), or the abnormal results of an investigation (e.g., laboratory findings, electrocardiogram). In clinical studies, an AE can include an undesirable medical condition occurring at any time, including run-in or washout periods, even if no study treatment has been administered. The term AE is used to include both serious and non-serious AEs.

• Serious Adverse Events:

A serious adverse event is an AE occurring during any study phase (i.e., screening, runin, treatment, wash-out, follow-up), at any dose of the study drugs that fulfills one or more of the following criteria:

- Results in death
- Is immediately life-threatening
- Requires in-patient hospitalization or prolongation of existing hospitalization
- Results in persistent or significant disability or incapacity

- Is a congenital abnormality or birth defect
- Is an important medical event that may jeopardize the patient or may require medical intervention to prevent one of the outcomes listed above.
- The causality of SAEs (their relationship to all study treatment/procedures) will be assessed by the investigator(s) and communicated to the FDA via MedWatch form, if applicable.
- 2. Recording of Adverse Events

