Once participants are started on study drug, monitoring for prolongation of QTc or development of polymorphic ventricular tachycardia is required. The Zio AT (iRhythm Technologies, Inc.) is a mobile cardiac telemetry device that allows continuous monitoring of the QTc interval and heart rhythm abnormalities. The Zio AT consists of a small transdermal patch that is applied on the participant's upper chest and a gateway device (size of a cell phone) that has to be kept within 10 feet of the participant. The ECG signal is transmitted to iRhythm technologies via the internet using the gateway. The participant does not have to change batteries or do anything to the device for the 10-day monitoring interval. We have used this device clinically and participant compliance is excellent. The rhythm is monitored continuously for arrhythmias and our EP-cardiology team will be notified immediately for any run of ventricular tachycardia (VT) greater than 4 complexes and other significant arrhythmias (pauses greater than 3 seconds, heart block, atrial fibrillation). We are monitoring for any run of VT since we have found that most episodes of torsade de pointes VT are preceded by shorter runs of polymorphic VT. The participant can also

trigger a transmission by pressing a small button on the transdermal patch if they experience any cardiac symptoms. We will monitor the QTc with this device. We will obtain a baseline transmission at the initial visit after the participant has been deemed to be eligible based on the Kardia Mobile 6L QTc measurement. We will ask the participant to do a transmission for QTc measurement 2 hours after the first dose of study drug. These will be reviewed and QTc measured by our EP cardiology team. We will then monitor the QTc interval twice a day at two predetermined times. This type of monitoring is equivalent to what can be done in the hospital on telemetry and in practice may be superior since the protocol will be strictly adhered to and measurements made by an electrophysiologist. If QT interval increases from baseline of > 60msec or QT > 500 msec, the medications, if still being taken, will discontinued at that time. Participant QT will be monitored every 6 hours until the interval returns to baseline. If a serous arrhythmia is detected during the continuous monitoring, the study cardiologist and participant will be promptly contacted, and the participant will be directed to seek medical treatment as appropriate.

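### The planned QT slope model does not measure QT prolongation during the 5 days of dosing; a baseline-adjusted day 1-5 contrast would

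*Combined protocol and SAP*

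**What the plan says.** Section 6.1 (Data Analysis, secondary outcomes) groups QT with the change variables: "change in Q-T interval, we will fit linear mixed effects models (similar to primary outcome". Of the primary model, 6.1 says: "The model will include a random slope and intercept, to account for within participant correlation". On the tested quantity it says: "Our primary hypotheses involve the change over time, which we will assess with the treatment by time interaction terms". It adds that from this model "we can estimate a treatment effect at any particular day". The power section (1.5) treats time as linear, since its second step is to "fit random slope and intercept models to the simulated data" and its third is to count rejections of the treatment-by-slope interaction.

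On exposure and measurement, section 1.3 says: "Treatment with the investigational agents or placebo will continue for 5 days". Section 1.3 B has QT measured through day 10. Section 4.7 E adds a baseline transmission and one 2 hours after the first dose, and then: "We will then monitor the QTc interval twice a day at two predetermined times". When a QT limit is crossed, study medication stops and, per 1.3 B, "Participant QTc intervals will be monitored every 6 hours until the interval returns to baseline".

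The analysis is by intention to treat. The documents give no QT analysis window, no non-linear time term, no named day for a QT contrast, and no rule for readings after day 5 or after a QT-triggered stop. Separately, secondary endpoint 7 in 1.3 F is a threshold: a change above 60 msec, or QT above 500 msec.

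**The concern.** A per-day slope suits viral load, which is expected to decay steadily. A drug effect on QT is different. It may appear with the first day's dosing, hold while drug is taken, and then persist or fade. About half of the scheduled readings fall after the last dose. A straight line through all of them mixes onset, plateau and washout into one number, and its sign and size need not reflect how far QT was prolonged on treatment.

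This matters because section 1.7 states that hydroxychloroquine prolongs QT and that no data assess the risks of the three drugs together. A null or negative slope could be read as reassurance. A mean shift of around 20 ms would mostly fall below the endpoint 7 thresholds, so the continuous analysis is where it should show.

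**Working it through.** The documents give no QT effect size, SD or power, so there is no QT figure to reproduce. Everything below that is not a schedule, sample size or half-life is an assumption.

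**Inputs from the documents.** 35 per arm (1.5). Dosing for 5 days (1.3). Readings at 0 h, 2 h and every 12 h to day 10 (1.3 B, 4.7 E), which gives 22 readings with mean time 4.78 days and Sxx = 215.6. Hydroxychloroquine half-lives of 22.4 days in blood and 123.5 days in plasma (1.2). If the QT effect followed those levels, the share left at day 10 would be 0.5^(5/22.4) = 86% or 0.5^(5/123.5) = 97%.

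**Assumed.** A true on-treatment effect of 20 ms, reached immediately, over 1 day or over 5 days, and decaying after day 5 with a stated half-life.

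**Step 1: what the interaction estimates.** It is the least-squares slope of the between-arm difference d(t): slope = Σ(t − 4.78)·d(t) / 215.6. In ms/day:

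| Onset | half-life 1 d | 3 d | 5 d | 22.4 d |
|---|---|---|---|---|
| Immediate | -1.93 | -1.01 | -0.58 | +0.17 |
| Over 1 day | -1.33 | -0.42 | +0.02 | +0.76 |
| Over 5 days | -0.27 | +0.64 | +1.08 | +1.82 |

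The on-treatment peak is 20 ms in every cell. The immediate-onset row shows the reason. If the effect never faded, the slope would be 20 × 4.78 / 215.6 = +0.44 ms/day, all of it from the single baseline reading. Any fading subtracts from that.

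**Step 2: chance of detection.** Simulation with 35 per arm, SD of 15 ms for both between-person and reading variation, no stopping, two-sided 5%. At the 22.4-day half-life the interaction was significant in about 11% of trials with immediate onset, about 80% with one-day onset and 100% with five-day onset. The baseline-adjusted day 1-5 mean was significant in 96-100% of trials in every onset and washout case. Its true value is 20 ms for the first two onsets. For the five-day ramp it is (4+6+8+10+12+14+16+18+20)/9 = 12 ms. Washout after day 5 does not enter it.

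**Step 3: with QT-triggered stopping.** Mixed model, 60 simulated trials per case, one-day onset, mean effect 20 ms, between-person SD 15 ms, residual SD 10 ms, stop above 60 ms, then 6-hourly readings, all included:

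| Half-life | mean slope, ms/day | significant | day 0-5 mean change, between arms |
|---|---|---|---|
| 1 d | -1.38 | 77% negative | +16.2 ms |
| 3 d | -0.61 | 63% negative | +17.6 ms |
| 22.4 d | +0.68 | 73% positive | +17.9 ms |

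**Step 4: the model's other outputs.** The fitted day-5 difference is intercept + 5 × slope. For the Step 1 cases it runs from 7.1 ms (five-day onset, 1-day half-life) to 18.4 ms (immediate onset, 22.4 days), against a true 20 ms at day 5. In Step 3 the fitted day-0 difference was 14.8 to 16.4 ms. Both stay positive.

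**Step 5: the extra 6-hourly readings.** In a separate simulation with full effect on days 1-5 that is gone by day 10, dropping them moved the slope from -1.18 to -1.08 ms/day. With an effect sustained to day 10 it moved from +0.05 to +0.22. Their influence is small.

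**The case against.** The strongest reply is that the plan is brief rather than wrong. Linear time for QT is inferred. The sentence naming the interaction speaks of the primary hypotheses, meaning viral load, and 6.1 says effects can be estimated at a chosen day. A day-5 contrast from the same fit would be positive. This limits the point but does not remove it. The interaction is the only contrast 6.1 ties to a hypothesis, no day is named for QT, and the fitted day-5 difference is itself attenuated.

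A reader might infer that the analysis will show QT shortening. That needs an effect that fades within days, which the documents do not give. Their hydroxychloroquine half-lives point instead to persistence and a slope that is near zero or positive. Persistence does not rescue the test, though, because detection then depends on the shape of onset rather than on the size of prolongation.

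A reader might also infer that the 6-hourly readings bias the result seriously. The documents describe them as participant monitoring and do not say they enter the analysis. Where they were included, they moved the slope little.

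**Conclusion.** The point holds in a limited form. On its natural reading, the planned QT model tests a quantity that is not on-treatment prolongation. The same 20 ms peak gives about -1.9 to +1.8 ms/day for washout half-lives of 1 to 22.4 days. At the stated blood half-life, the chance of a significant interaction runs from about 11% to 100% depending on onset alone. A baseline-adjusted day 1-5 mean avoids this, using data already planned.

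A reader might go further and say the trial's QT safety conclusion would be wrong. The documents do not support that. Endpoint 7 is a proportion that does not depend on a slope and would still capture large prolongations, QTc is reviewed twice daily by the electrophysiology team, and the DSMB reviews adverse events. What is at risk is the continuous QT result.

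All effect sizes, SDs, onset shapes and QT washout rates are assumptions. Linear time and the use of all readings are inferred from 6.1 and 1.5.

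**What to change.** In 6.1, take QT out of the sentence that ties it to the primary model. Define the QT contrast as the between-arm difference in change from baseline over days 1-5, as (i) the mean and (ii) the maximum, adjusted for the baseline reading. Include all randomized participants and use the scheduled twice-daily readings whether or not drug was stopped. A mixed model with categorical time and a named on-treatment contrast would serve equally well. Report days 6-10 as a separate period, keep any unscheduled 6-hourly readings to listings, and keep endpoint 7 as a proportion.

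State also whether the analysed variable is QT or QTc. Sections 1.3 B and 4.7 E word the change-from-baseline limit differently on this, and the two must be reconciled.

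The cost is a wording change and one simple model on data already collected. The single-slope summary for QT is given up.
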